9.1.4 Sample Collection and Schedule during Follow-up

Patients who received adjuvant PD 0332991

Research blood includes the collection of plasma, serum, and whole blood for cfDNA. Research blood will be collected on Day 1 +/- 3 days of adjuvant Cycles 1 and 12 and at the end of treatment (either end of Cycle 23 or end of the last cycle received if the patient ends treatment early). Additional research draws will take place annually for 3 years following the last dose of PD 0332991 (+/- 8 weeks).

All other patients

Research blood includes the collection of plasma, serum, and whole blood for cfDNA. Research blood will be collected 1 year post surgery, then annually for a total of 5 years following surgery or until recurrence (whichever comes first).

Blood for all patients will be collected as follows:

- 10 mL in an EDTA (purple top) tube for plasma to be stored at -80°C; to process the blood samples to plasma, centrifuge the blood samples at approximately 4°C at 1700xg for approximately 10 minutes.
- 10 mL in a clot (red top) tube for serum to be stored at -80°C
- 10 mL each in 2 cell-free DNA BCT tubes to be stored at room temperature and shipped same day to the Washington University Tissue Procurement Core Facility; the cell free DNA collection BCT tube (provided) should be mixed several times and labeled with the patient's study number, date of birth, and collection date and time. Whole blood specimens are shipped and must be received by the Washington University Tissue Procurement Facility within 48 hours of the time of collection.

9.1.5 Shipment of Samples

All samples should be labeled with institutional surgical pathology number (tumor

samples), study number, patient ID number patient initials, sample collection date and time and be accompanied by the completed specimen submission forms (Appendix F/K/L (as appropriate)).

All samples should be shipped to the Wash U Tissue Procurement Core Facility.

Specimens may be sent to the Wash U Tissue Procurement Facility on Monday through Thursday for next day delivery. **The Bank cannot receive specimens on Saturdays, Sundays, or holidays. Do not send specimens on Friday, Saturday, or the day before a holiday.**

The institution is expected to pay the cost of mailing specimens and will be reimbursed through capitation fees set for each individual study.

Arrange for Federal Express pick-up through your usual institutional procedure. Ship specimens to the address below:

Wash U Alliance/ACOSOG-CBS/TPS
[name]
[name]
[contact]
E-mail: [contact]

On the day that specimens are sent to the specimen bank, please contact the bank by phone, fax, or e-mail to notify what is being sent and when the shipment is expected to arrive.

9.2 Real Time Integral Biomarker Studies

Note that the PIK3CA (Gene ID: 5290) hot spot sequencing assay that covers exons 1, 4, 7, 9 and 20, is done while the patient was pre-registered to the NCI 9170 trial or through this trial. Briefly, sequencing of these 5 exons and exon-intron splice junctions should be performed using the established protocol at the CLIA certified GPS@WU, a CAP-accredited (#27556-03) and CLIA-licensed (#26D0698685) laboratory environment under the unified supervision by faculty in the Departments of Genetics and Pathology and Immunology at Washington University.

Tumor biopsy will be sectioned and H&E stained for evaluation of tumor cellularity by a pathologist and processed to tumor DNA and RNA extraction at Washington University once it arrives at the Alliance Central Specimen Bank. The first of the two formalin fixed and paraffin embedded (FFPE) tumor cores will be sectioned and stained by H&E to assess for tumor cellularity. If the total normal of tumor nuclei is greater than 75% in the biopsy, serial sections will be immediately prepared for DNA and RNA extraction. If tumor cellularity is less than 75%, the second frozen core will be evaluated. In cases where both FFPE tumor biopsies contain less than 75% neoplastic cellularity, macro- or micro-dissection of tumor rich area will be performed if there is sufficient tumor. If neither

baseline sampling core contains sufficient tumor cellularity, the frozen tissue will be examined. If needed a second biopsy may be required if the patient consents.

High quality DNA sequence reads that are concordant on both strands will be analyzed from each amplicon. Variant calls (as compared to reference sequence) will be reported as a qualitative / non-ordered categorical result. The position (nucleotide, exon, amino acid, and protein domain), sequence variant, and predicted change (if any) in corresponding amino acid sequence will be reported. If a non-synonymous variant identified has never been reported to be a somatic mutation, germ-line DNA will be sequenced from the same patient to determine whether this is a somatic mutation or a polymorphism. The result will be further classified as: 1) Previously described somatic mutation; 2) Novel somatic mutation, not a germ-line polymorphism. Results will be emailed to the study coordinator at the participating site. Contact [contact] for questions related to the sequencing result.

Patients with or without a somatic mutation in PIK3CA hotspot region are eligible for the trial.

9.3 Tumor Ki67 Assessment on Cycle 1 Day 1 (Pre-PD 0332991) and Cycle 1 Day 15

9.3.1 Rationale

If Ki67 is over 10% on Cycle 1 Day 15, patient will be taken off the study drug therapy and recommended to either immediate surgery or neoadjuvant chemotherapy. If Ki67 is 10% or less, the patient will continue therapy for a total of 5 cycles of combination PD 0332991 and endocrine therapy.

9.3.2 Tissue Processing and Ki67 Analysis

Upon receipt of the specimen, the 2 fixed biopsy specimens (A & B) at each time point will be further processed for tumor Ki67 analysis at the CLIA certified Anatomic and Molecular Pathology Core Labs at Barnes Jewish Hospital at St. Louis (CLIA number 26D2013203). After embedding in paraffin, one section from the tumor block will be stained with H&E to assess biopsy adequacy. Another section from the block will be incubated with antibody against Ki67 (clone 30-9) and then assayed using the Ventana Benchmark platform. The block and any remaining sections will be returned to the Tissue Procurement Core Facility at the completion of testing. Both cores will be reviewed and will be taken into account for the scoring. Ki67 scoring is reported as a quantitative/continuously distributed value.

9.3.3 Ki67 Scoring and Reporting

Ki67 scoring will be performed using a standard SOP established at the CLIA laboratory, with the result expressed as immunoreactive over total numbers of cells. The Ki67 data for C1D15 biopsy is available real time to the treating physician and

the patients. Patients will be continued on protocol therapy while awaiting analysis results. Results of tumor Ki67 will be reported within 10 working days upon receipt of the samples. Wash U Path Coordinator will email and fax the results to both the CRA listed on Specimen Submission CRF that is sent with the tissue samples and Wash U CRA. Contact [contact] for questions related to the Ki67 result.

Note: If the biopsy yielded no tumor cells, the patient may continue on study drug therapy or proceed with a second biopsy for Ki67 determination.

9.4 Laboratory Correlative Studies

Laboratory correlative studies are performed on leftover tumor specimens following the integral biomarker analysis (Section 9.2) from baseline, on Cycle 1 Day 1 (pre-PD 0332991), Cycle 1 Day 15, and on surgical specimens.

9.4.1 To assess tumor cell apoptosis on serial tumor specimens

Methods: FFPE tumor blocks obtained from biopsies at baseline and post therapy will be sectioned at 5 micron sections for immunohistochemistry analysis of cleaved caspase 3 or TUNEL staining with established method at the Study PI and Co-PI's laboratory. Apoptotic index will be calculated as the percentage of tumor cells staining positive for apoptotic markers (either cleaved caspase 3 or TUNEL staining).

9.4.2 To assess Ki67 level on serial tumor biopsies

Methods: Ki67 at baseline, Cycle 1 Day 1 (pre-PD 0332991), Cycle 1 Day 15, and surgery will be performed at the CLIA certified Anatomic and Molecular Pathology (AMP) facility at Washington University on FFPE sections of serially collected tumor biopsies. Ki67 index will be calculated as the percentage of tumor cells stained positive at each time point.

9.4.3 To assess effect of PD 0332991 on markers of tumor cell senescence

Methods: Candidate proteins important for senescence including p16, cyclin D1, activated mTOR (such as pS6), IL6, senescence associated beta-galactosidase, FOXM1 phosphorylation, will be examined by IHC.

9.4.4 To examine the pharmacodynamic effect of PD 0332991 in combination with endocrine therapy on Cdk4/6 Rb signaling activities

Methods: The pharmacodynamic effect of PD 0332991 in combination with anastrozole on Cdk4/6-Rb signaling will be assessed by phosphoproteomics and immunohistochemistry analysis of pRB and other candidate molecules on serial tumor biopsies.

9.4.5 Assessment of serum estradiol level before and following PD 0332991

Sensitive estradiol level in premenopausal women will be tested in the clinical laboratory at the end of 4 weeks of anastrozole (or in combination with goserelin) (at baseline), Cycle 1 Day 15, and surgery.

9.4.6 Explore potential markers of sensitivity and resistance

In preclinical studies, RB proficient cell lines with low p16 expression were found to be most sensitive to PD 0332991 in ovarian cancer. In addition, copy number variations of CDKN2A, RB, CCNE1, CCND1 were associated with response[102]. Therefore, tumor specimens collected on Cycle 1 day 1 will be analyzed for the protein expression of these genes by immunohistochemistry. Gene copy number changes will be assessed by aCGH method. These studies will be performed in the study PI and Co-PI's laboratory. Other studies include hypothesis generating exploratory DNA and RNA studies as well as proteomic analysis.

9.4.7 Pharmacokinetics

Ten mL of blood will be drawn into each of 2 K₂EDTA tubes at the following time points to evaluate the concentrations of PD 0332991 and the effect of PD 0332991 on the concentrations of anastrozole:

- Prior to initiation of PD 0332991 but after patients have taken anastrozole alone or in combination with goserelin for at least 2 weeks (this could be done on Cycle 1 Day 1):
 - pre-dose of anastrozole
 - 90 minutes following this same dose of anastrozole
- Cycle 1 Day 15 (may take place up to Day 21 if samples are missed)
 - prior to both anastrozole and PD 0332991
 - 90 minutes following administration of both drugs

Process blood to plasma within 30-45 minutes by centrifuging in a refrigerated centrifuge (1700 x g for about 10 minutes at 4°C) within 1 hour of collection. The collection tube containing PD 0332991 should be covered with aluminum foil to protect from light. Transfer plasma into pre-labeled amber polypropylene storage cryovials and store at -20°C. Ship the samples on dry ice to the following address:

Wash U Alliance/ACOSOG-CBS/TPS
[name]
[name]
[contact] // E-mail: [contact]

At the completion of the 1st stage and the 2nd stage of the study, batched samples will be sent by Washington University CRA to the following addresses for analysis:

For PD 0332991 analysis:

[name] c/o PPD
[name]
[name]
[contact] // E-mail: [contact]

For anastrozole analysis:

[name] c/o Covance Laboratories, Inc.
[name]
[name]
[contact] // E-mail: [contact]

10.0 STUDY CALENDARS

10.1 Pre-Registration and Cycle 0 Calendar

This applies only to the PIK3CA WT and Mutant Cohorts (closed as of Amendment #7).

	≤ 14 days prior to pre-registration	Pre-Registration	≤ 14 days Pre-Anastrozole	Cycle 0 Day 1 ^A (≤ 7 days post pre-registration)
TREATMENT				
Anastrozole				Days 1-28 ^B
Goserelin ^C				X
CLINICAL ASSESSMENT				
H&P, PS	X		X	
Clinical measurements of breast lesions ^D	X		X	
Adverse event assessment				
CBC and differential	X		X	
Serum chemistry ^E	X		X	
RADIOLOGY				
Mammogram and ultrasound of breast and axillary masses ^F	X ^F			
SAMPLE COLLECTION				
Tumor biopsies ^R			X ^G	
Research blood samples ^R			X ^H	

- A. Cycle 0 Day 1 is to start ≤ 7 days post pre-registration. Tumor biopsy and blood collections must be done prior to the start of anastrozole.
- B. All effort is to be made to keep Cycle 0 length at 28 days, but up to 42 days of Cycle 0 therapy is allowed prior to the start of Cycle 1 Day 1 due to delays in PIK3CA sequencing result or scheduling difficulties. In this situation, goserelin should be administered every 28 days throughout the study regardless of cycle days.
- C. In premenopausal women only
- D. Using a standard cm calibrated caliper, tape or ruler, the longest axis and the perpendicular axis of the tumor are to be measured and recorded in metric notation. In patients with synchronous lesions, it is recommended that both lesions be measured and biopsied the same if they are both >1cm with at least one dimension.
- E. Serum chemistry is albumin, alkaline phosphatase, total bilirubin, bicarbonate, BUN, calcium, chloride, creatinine, glucose, potassium, total protein, SGOT/AST, SGPT/ALT, sodium
- F. Mammogram and ultrasound of the diseased breast must be completed within 42 days of pre-registration. Imaging studies must include bidimensional breast tumor measurements, although retrospective measurement of the imaging study is allowed after patient pre-registered on the study.
- G. Pre-anastrozole core biopsies for correlative studies are required prior to the initiation of anastrozole therapy. Samples obtained at the time of diagnosis before registration to this trial (for other studies) may be submitted if they were collected according to the tissue acquisition instructions in Section 9. It is advised that the baseline samples are harvested during ultrasound guided clip placement to optimize tissue accrual.
- H. For patients pre-registered to this trial only.
- R. Research funded

10.2 Neoadjuvant Study Treatment Calendar (ALL Cohorts)

	≤ 14 days prior to registration	C1D1 ^A	C1D15 ±1 day	C2-5 D1±3 days	3 (+/-1) days prior to surgery	Off Study - Progression	Surgery ^B	Post-surgery ^C
TREATMENT								
Anastrozole ^E		Daily until the day of surgery (if no progression)						
Goserelin ^E		Every 28 days (if no progression)						
PD 0332991 ^F		3 weeks on and 1 week off ^{G,T}			D/C			
CLINICAL ASSESSMENT								
H&P, PS	X	X		X		X		X
Clinical meas. of breast lesions ^J	X	X		X		X		Exam
Adverse event assessment	X	X		X		X		X
CBC + differential	X			X	X ^Y			X
Serum chemistry ^K	X			X				X
Serum pregnancy test ^L		X			X	X		
Drug compliance assessment				X				
EKG (lead II) ^N	X						X	
RADIOLOGY								
Mammogram and US of breast and axillary masses ^O	X ^H			X ^H		X		
SAMPLE COLLECTION								
Tumor biopsies ^R		X ^W	X ^P	X ^Q		X ^S	X	
Research blood ^R		X ^U	X ^{P,V}			X ^S	X	

- A. C1D1 office visit, labs, EKG, as well as pre-PD 0332991 tumor biopsies may be done within 14 days prior to C1D1.
- B. Please refer to section 5.1. Surgery occurs between Cycle 5 day 11 and day 13 in patients who received Cycle 5 treatment. In patients who did not receive Cycle 5 treatment, surgery occurs 3 to 5 weeks following the last dose of PD 0332991.
- C. 30-60 days post-surgery, then yearly to document recurrence and survival for 5 years.
- E. Anastrozole (and goserelin if premenopausal) should have been started at least 28 days prior to C1D1 **(only applies to PIK3CA Mutant and Wild Type cohorts).
- F. Patients will keep a pill diary (Appendix D).
- G. If C1D15 Ki67 is > 10%, patient will discontinue PD 0332991 and be observed for AEs 30-60 days following the last dose, then followed per protocol. Further treatment is at the discretion of the treating physician.
- H. Prior to start of PD 0332991 (within 12 weeks prior to registration) and at the end of cycle 4 before surgery.
- J. 2D measurements of the breast lesion should be performed. Using a standard cm calibrated caliper, tape or ruler, the longest axis and the perpendicular axis of the tumor are to be measured and recorded in metric notation. In patients with synchronous lesions, it is recommended that both lesions be measured and biopsied the same if they are both >1cm with at least one dimension; otherwise, the dominant mass is followed clinically and by Ki67
- K. Serum chemistry is albumin, alkaline phosphatase, total bilirubin, bicarbonate, BUN, calcium, chloride, creatinine, glucose, potassium, total protein, SGOT/AST, SGPT/ALT, sodium
- L. In premenopausal women only
- N. EKG will be performed at baseline, pre-surgery, and as needed. Surgery may be delayed if QTc prolongation has occurred.
- O. Mammogram and ultrasound of the diseased breast must be completed within 12 weeks prior to registration. Imaging studies must include bidimensional breast tumor measurements, but retrospective measurement is allowed in the study.
- P. C1D15 biopsy and blood draw may be done up to C1D20 for scheduling convenience, although C1D15 is strongly preferred.
- Q. Optional biopsy on C2D15, C3D15, or C4D15 in patients with indeterminate Ki67 on C1D15 biopsy or who missed the C1D15 biopsy.
- R. Research funded. Research blood samples are mandatory except where indicated.
- S. Optional
- T. If counts recover within 3 weeks of the end of C4, re-start PD 0332991 for 10 to 12 doses (C5) (last dose to be the day before surgery).
- U. PKs to be drawn on a day prior to initiation of PD 0332991 (may be C1D1) pre-anastrozole and again 90 minutes post-anastrozole. Other research blood include serum, plasma, whole blood for germline DNA and whole blood for circulating tumor DNA is also collected on C1D1. Details are described in Section 9.1.2. PK samples are not required in the endocrine resistant cohort.
- V. PKs to be drawn pre-dose of both drugs and again 90 minutes post-dose of both drugs. PK samples are not required in the endocrine resistant cohort.
- W. Not required in endocrine resistant cohort if a research biopsy was performed prior to registration or an archival tumor block is available
- Y. Only required in patients who are in Cycle 5.

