1.6.2 Pharmacodynamics/kinetics

In females, a down-regulation of the pituitary gland by chronic exposure to goserelin leads to suppression of gonadotropin secretion, a decrease in serum estradiol to levels consistent with the postmenopausal state, and would be expected to lead to a reduction of ovarian size and function, reduction in the size of the uterus and mammary gland, as well as a regression of sex hormone-responsive tumors, if present. Serum estradiol is suppressed to levels similar to those observed in postmenopausal women within 3 weeks following initial administration; however, after suppression was attained, isolated elevations of estradiol were seen in 10% of the patients enrolled in clinical trials. Serum LH and FSH are suppressed to follicular phase levels within four weeks after initial administration of drug and are usually maintained at that range with continued use of goserelin. In 5% or less of women treated with goserelin, FSH and LH levels may not be suppressed to follicular phase levels on day 28 post treatment with use of a single 3.6 mg depot injection. In certain individuals, suppression of any of these hormones to such levels may not be achieved with goserelin. Estradiol, LH and FSH levels return to pretreatment values within 12 weeks following the last implant administration in all but rare cases [AstraZeneca, Package Insert].

The pharmacokinetics of goserelin have been determined in both male and female healthy volunteers and patients. In these studies, goserelin was administered as a single 250 µg (aqueous solution) dose and as a single or multiple 3.6 mg depot dose by subcutaneous route. The absorption of radiolabeled drug was rapid, and the peak

blood radioactivity levels occurred between 0.5 and 1.0 hour after dosing.

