in the PIK3CA WT cohort and all 15 (100%, 90% CI: 82-100%) patients in the PIK3CA mutant cohort. The study met its primary endpoint of achieving a CCCA rate of 66% in C1D15. In addition, 26 patients who did not achieve CCCA with anastrozole alone on C1D1 achieved complete CCCA in C1D15 post 2 weeks of combination therapy. These data justify the evaluation of PD 0332991 in the adjuvant setting. The international PALLAS (PALbociclib CoLlaborative Adjuvant Study) trial is currently enrolling patients with high risk ER+ HER2- breast cancer to receive 2 years of palbociclib (PD 0332991) in the adjuvant setting. However, patients who received neoadjuvant PD 0332991 (palbociclib) are not eligible for the adjuvant PALLAS trial. We therefore propose to include in this trial the option of adjuvant PD 0332991 with anastrozole for 23 cycles after chemotherapy and radiation therapy for those who derived benefit from PD 0332991 in the neoadjuvant setting in this trial. This includes:

- The 26 patients who achieved complete cell cycle arrest only after the addition of PD 0332991 (C1D1 Ki67 $>2.7\%$ and C1D15 Ki67 $\leq 2.7\%$) (in the PIK3CA WT, mutant, or unknown cohorts).
- Patients who have a Ki67 $\leq 10\%$ on C1D15 biopsy in the endocrine resistant cohort (including patients enrolled prior to activation of Amendment #7).

All patients (with the exception of those who withdraw consent for follow-up and those who did not undergo surgery) will be followed for invasive disease recurrence and overall survival for 5 years in the adjuvant setting or until recurrence (whichever comes first). Blood will be drawn for serum, plasma, and circulating cell-free DNA (cfDNA) yearly.

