1.9 Correlative Studies Background

1.9.1 Early Tumor Ki67 Assessment during Neoadjuvant Endocrine Therapy to Determine Treatment Response

In this trial, we plan to perform tumor biopsy to assess Ki67 following one month of endocrine therapy (pre-PD 0332991) and 2 weeks on combination of PD 0332991 and anastrozole (Cycle 1 Day 15). This is based on data from previous neoadjuvant endocrine trials which indicated that 2-4 week tumor Ki67 expression on neoadjuvant endocrine therapy is predictive of individual patient outcome long term[11, 25, 26]. In the IMPACT trial, 2-week Ki67 was a significant independent predictor of RFS (HR = 1.95; 95% CI = 1.23–3.07; $P = .004$) [25]. The 5-year RFS rates were 85%, 75%, and 60% for the lowest, middle, and highest values of 2-week Ki67 expression, respectively[25]. In the P024 trial, while baseline Ki67 was not associated with relapse, post 16-week treatment Ki67 levels had a robust association with RFS (HR = 1.4, CI = 1.2–1.6 per natural log unit increase; $P < .001$), and breast cancer-specific survival (HR = 1.4, CI = 1.1–1.7; $P = .009$) [11].

To further investigate these findings, Ellis et al examined the interaction between Ki67 levels and a PAM50-based definition of luminal A breast cancer versus luminal B breast cancer. By using ROC methodology, a cut point of Ki67 10% served as the best surrogate for the LumA versus LumB distinction [99]. The 10%

Ki67 cut point was then applied to the baseline and early on-treatment data in two data sets (Table 2), Preoperative Letrozole study (POL) [13] and IMPACT trial [25]. At baseline the dichotomized Ki67 definition was not significantly predictive for surgical Ki67 level, PEPI score or RFS in these modest sized sample sets. In contrast, high levels of Ki67 on the one month POL samples predicted a higher level of Ki67 in the surgical samples at four months after treatment initiation ($P=.01$), a poorer PEPI score ($P=0.01$), a smaller number of patients in the PEPI-0 group ($P=0.08$) and worse RFS ($P=0.003$). IMPACT data confirmed that a 2-week Ki67 $>10\%$ predicted higher Ki67 in the surgical specimen ($P=0.001$), a poorer PEPI score ($P=0.001$), smaller numbers of patients in the PEPI-0 group ($P= 0.004$) and worse RFS ($P=0.008$) (Table 2.3).

Table 2 Early Ki67 Assessments and Outcome in IMPACT and POL Trials		
POL 4W Ki67	% PEPI 0	RFS (events)
$>10\%$	1/19 (5%)	5/21 (23%)
$\leq 10\%$	10/36 (28%)	1/41 (2.4%)
P Value	$P=0.08$ (Fisher)	$P=0.003$ (log rank)

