IMPACT 2W Ki67	% PEPI 0	RFS (events)
$>10\%$	0/32 (0%)	9/35 (26%)
$\leq 10\%$	21/101 (21%)	13/118 (11%)
P Value	$P=0.004$ (Fisher)	$P=0.008$ (log rank)

In this trial, to avoid futile therapy, we plan to obtain tumor biopsy post 2 weeks of PD 0332991 in combination with anastrozole. Patients whose Day 15 Ki67 $>10\%$ will be considered resistant to the combination therapy. These patients will be recommended alternative therapies such as immediate surgery or neoadjuvant chemotherapy. The pre-PD 0332991 Ki67 will not be used for clinical decision making since PD 0332991 will be added to the treatment regimen. It is, however, important to obtain the pre-PD 0332991 Ki67 since this allows a comparison between anastrozole alone and the combination of anastrozole and PD 0332991 on the degree of Ki67 suppression.

1.9.2 To Assess Tumor Cell Apoptosis on Biopsies Taken Pre-PD 0332991 and Cycle 1 Day 15

We will investigate whether there is an increase in tumor cell apoptosis with the combination of PD 0332991 and anastrozole (or anastrozole in combination with goserelin). Anastrozole 1mg daily dosing reduced estradiol level by 70% by 24 hours and by approximately 80% after 14 days of daily dosing [AstraZeneca, Package Insert], therefore, full estrogen deprivation is expected by 28 days of anastrozole administration. In the case of goserelin, serum estradiol is suppressed to levels similar to those observed in postmenopausal women within 3 weeks

following administration. In addition, only 5% or less of women treated with goserelin, FSH and LH may not be suppressed to follicular phase levels on day 28 post treatment with a single 3.6mg depot injection [AstraZeneca, Package Insert].

1.9.3 To Assess the Degree of Ki67 Suppression before (Pre-PD 0332991) and after PD 0332991 (Cycle 1 Day 15)

The degree of Ki67 suppression following 2-4 weeks of therapy has been associated with the effectiveness of endocrine agents or the combination of endocrine agent with an mTOR inhibitor. In the IMPACT trial, suppression of Ki67 after 2 and 12 weeks was significantly greater with anastrozole than with tamoxifen ($P = 0.004$) which mirrored the result based on RFS in the ATAC trial [100]. These data indicate that Ki67 response early on therapy could potentially be employed as a measurement of treatment efficacy.

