Adverse Events: All eligible patients that have initiated treatment will be considered evaluable for assessing adverse event rate(s). The maximum grade for each type of adverse event will be recorded for each patient using the NCI-CTCAE v4.0, and frequency tables will be reviewed to determine patterns. Additionally, the relationship of the adverse event(s) to the study treatment will be taken into consideration.

Ki67 suppression on Cycle 1 Day 1, Cycle 1 Day 15 and surgery: Following the approach of Dowsett et al. [26], the percent change in the Ki67 level from baseline will be determined on the log scale. A 95% t-confidence interval for the mean percent change in the Ki67 level from baseline will be constructed (if appropriate). The rate of complete cell cycle arrest on C1D1, C1D15, and surgery will be described by contingency tables compared by McNemar tests. Using trajectory analysis, we will also assess the association between distinct patterns of Ki67 change over time and clinical outcomes. Specifically, trajectory groups will be formulated to describe clusters of individuals with similar temporal patterns of Ki67 over time using finite mixture models with SAS procedure TRAJ. This method enables identification of the number of discrete trajectory types, and characterization of the shape and estimation of the prevalence of each type. We will choose the best models based on statistical tests (including Bayesian and Akaike information criterion, each of which test goodness-of-fit) and clinical judgment.

To assess the long term outcomes of patients treated in this trial: The long-term outcomes (i.e., pathologic complete response (pCr), local and distant recurrence, etc, as defined in section 12.4) will also be assessed in the PIK3CA wild and mutnt cohorts (separately and combined) and the endocrine resistant cohort, respectively. The categorical outcome will be summarized using contingency tables and compared by Fisher's exact test, while the time-to-event outcomes will be described using Kaplan-Meier product limit estimators and compared by log-rank test.

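### The C1D1 biopsy may be taken from about day 14 of endocrine therapy, so the C1D1-to-C1D15 comparison can absorb an unknown amount of endocrine-only Ki67 suppression

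*Combined protocol and SAP*

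**What the plan says.** The run-in is meant to separate the effect of anastrozole from that of PD 0332991. The documents describe the timing of the pre-PD 0332991 sample in several ways:

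- Section 1.9.1: "we plan to perform tumor biopsy to assess Ki67 following one month of endocrine therapy", with a second biopsy after two weeks of the combination.
- Section 1.9.5: the RB sample at the same time point follows one cycle of anastrozole alone.
- Section 9.1.2: the table note equates the pre-PD 0332991 time point with C1D1.
- Section 10.2, footnote A: "pre-PD 0332991 tumor biopsies may be done within 14 days prior to C1D1".
- Section 10.2, footnote E: in the PIK3CA wild type and mutant cohorts, anastrozole (and goserelin if premenopausal) "should have been started at least 28 days prior to C1D1".
- Section 10.1, footnote B: "up to 42 days of Cycle 0 therapy is allowed prior to the start of Cycle 1 Day 1".
- Section 10.2, footnote P: the C1D15 biopsy may slip to C1D20.

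Section 15.5 then uses the value by its visit label: "The rate of complete cell cycle arrest on C1D1, C1D15, and surgery will be described by contingency tables compared by McNemar tests". It sets no minimum time on endocrine therapy at the biopsy, makes no adjustment for that time, and plans no sensitivity analysis. Section 1.8 relies on the same contrast when it reports "26 patients who did not achieve CCCA with anastrozole alone on C1D1" who had arrested by C1D15.

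**The concern.** Section 1.9.1 says the pre-PD 0332991 Ki67 is collected so that anastrozole alone can be compared with the combination. That comparison is clean only if endocrine suppression has levelled off by the first biopsy. The protocol's own reasoning gives times for this. In Section 1.9.2, "full estrogen deprivation is expected by 28 days of anastrozole administration". For goserelin, Section 1.6.2 states: "Serum estradiol is suppressed to levels similar to those observed in postmenopausal women within 3 weeks following initial administration". Section 1.6.1 adds that estradiol rises before it falls.

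A biopsy near day 14 comes before both times. If Ki67 was still falling under endocrine therapy, the C1D1 value would read higher than a true day-28 value. The further fall would then be credited to PD 0332991 in Secondary Objective 3 and in the Ki67 suppression analysis. Some women could also be counted among the 26 who arrested only after PD 0332991 was added, a label that Section 3.5.1 uses to define part of the adjuvant cohort.

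**Working it through.** **1. The plan's own timing.** A 28-day Cycle 0 plus 14 days of Cycle 1 gives 28 + 14 = 42 days of anastrozole at C1D15. This matches the 6 weeks of anastrozole and 2 weeks of PD 0332991 stated in Section 1.8. The planned interval between the two biopsies is 42 − 28 = 14 days, all on PD 0332991.

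**2. The timing that the footnotes allow.** Let R be the run-in before C1D1 (28 to 42 days; footnote E of 10.2 and footnote B of 10.1). Let L be the lead time of the biopsy (0 to 14 days; footnote A).

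- Endocrine exposure at the biopsy = R − L. Minimum 28 − 14 = 14 days; maximum 42 − 0 = 42 days.
- Interval to the C1D15 biopsy = 14 + L, at most 28 days. On C1D20 it is 19 + L, at most 33 days.
- Days on PD 0332991 within that interval: 14, or 19 on C1D20. The other L days, up to 14, are on endocrine therapy alone.
- Exposure falls below 28 days only if L > R − 28. With R = 28, any lead does this. With R = 42, no permitted lead does.

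**3. What uses the C1D1 value.** The primary test does not. It compares the C1D15 arrest rate with 44%. Its rule reproduces: for n = 33 and success at 20 or more, the exact binomial gives one-sided alpha 0.0408 at 44% and power 0.8005 at 66%, with no C1D1 term. The uses are Secondary Objective 3 (McNemar), the Ki67 change analysis and the 26 converters. The documents state no sample size or power for the C1D1 versus C1D15 comparison.

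**4. Sensitivity of the paired comparison.** Section 1.8 gives 39 of 45 arrested at C1D15 and 26 converters. Two things are assumed: that all 45 have a paired C1D1 value, and that c patients lost arrest between the biopsies. The documents do not give c; it can be at most 45 − 39 = 6.

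- Paired difference = (26 − c)/45: 57.8 percentage points at c = 0 and 20/45 = 44.4 points at c = 6.
- Each conversion that in truth belonged to the longer run-in lowers the difference by 1/45 = 2.2 points.
- The exact two-sided McNemar p-value first exceeds 0.05 when k of the 26 conversions are reclassified:

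| Losses c | k | Remaining converters | p |
|---|---|---|---|
| 0 | 21 | 5 | 0.0625 |
| 3 | 15 | 11 | 0.0574 |
| 6 | 10 | 16 | 0.0525 |

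Significance is fairly robust. The estimate and the individual labels are not protected in the same way.

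**The case against.** The strongest reply is that two weeks is a tolerance the protocol accepts throughout. Section 1.9.1 rests the biopsies on Ki67 at 2 to 4 weeks, the 44% control in Section 15.3 was measured at 2 to 4 weeks, and Section 3.4.1 accepts a Ki67 after at least two weeks of endocrine therapy. The 28-day statement belongs to the apoptosis rationale, and the same paragraph puts estradiol about 80% down after 14 days. Section 1.5.2 has plasma anastrozole near steady state at about 7 days. This stands: for postmenopausal women, little further suppression after day 14 is plausible. It does not remove the internal disagreement about timing, nor show that Ki67 is flat between weeks 2 and 4.

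Second, goserelin patients may be partly protected. Sections 3.2.1 and 3.3.1 require postmenopausal-range estradiol within 7 days before registration, Section 1.9.7 places the check after Cycle 0, and Section 4.2 bars any protocol intervention before registration. If a research biopsy counts as an intervention, suppression is documented first. The text does not define the term, so the protection is possible, not assured.

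Third, a biopsy exactly on C1D1 still leaves two further weeks of anastrozole in an uncontrolled before-after contrast. That is true; the window adds to this weakness.

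A reader might also infer that footnote A should be rewritten for the open cohort. The documents do not support that. The endocrine resistant cohort has no Cycle 0 and no 28-day rule, and footnote W waives its C1D1 biopsy if an earlier research biopsy or an archival block exists. In the closed cohorts a rewrite cannot change biopsies already taken.

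**Conclusion.** The concern holds as a gap in the secondary analysis of the PIK3CA wild type and mutant cohorts. The calendar permits a pre-PD 0332991 biopsy after 14 to 42 days of endocrine therapy, and an interval of up to 28 days (33 with C1D20) where 14 is intended. Section 15.5 does not account for either. If endocrine suppression was still developing, the bias enlarges the apparent PD 0332991 effect; this is most plausible in the first three weeks of goserelin.

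The size is unknown. The documents give no count of early biopsies, no count of premenopausal women and no Ki67 data at 2 versus 4 weeks.

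Two stronger readings are tempting and unsupported. One is that the PD 0332991 effect has in fact been inflated: the plan permits this but nothing shows it. The other is that some definite number of the 26 conversions is spurious. Any such number needs both the share biopsied early and the share of those who would have arrested by day 28. Neither is reported, and zero cannot be excluded. The primary result is untouched, and loss of significance in the paired test would need 10 to 21 reclassified conversions under the assumptions above.

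**What to change.** In Section 15.5, for the PIK3CA wild type and mutant cohorts:

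1. Compute days on anastrozole, and on goserelin where given, at the pre-PD 0332991 biopsy from the recorded collection dates, and report their distribution.
2. Repeat the C1D1 versus C1D15 McNemar test and the Ki67 change analysis without biopsies taken before day 28 of the run-in. For premenopausal women, exclude at minimum those taken before three weeks of goserelin.
3. Report how many of the 26 conversions rest on an early biopsy.

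Reconcile Sections 1.9.1, 1.9.5, 9.1.2 and 10.2 on when this biopsy is taken.

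The cost is one derived variable and one sensitivity analysis. The collection date is already a field on the biospecimen submission form, and no patient procedure is added. The downside is fewer pairs, and so a wider interval, in the restricted analysis.
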